3.5.2 Data Storage

Study documents will be stored securely by the Chief Researcher. Documents will be kept in a dedicated lever-arch file and will be arranged sequentially according to study number. All study documents relating to a single patient will be stored together.

3.5.3 Data Inspection

In case of incomplete data in Section B of the Data Collection Form, the chief researcher will review the following source documents in the order listed to obtain the information:

Missing data on medication given intra-operatively:	
 1. Blue anaesthesia report card 2. Nursing theatre record 3. Theatre record book
Missing data on medication given post-operatively:	
 1. Blue anaesthesia report card 2. Nursing theatre record
Missing data on anaesthesia start/end times:	
 1. Blue anaesthesia report card 2. Nursing theatre record 3. Datex-Ohmeda Aisys CS2 stored history 4. Theatre record book
Missing data on vapour start/end times:	
 1. Blue anaesthesia report card 2. Datex-Ohmeda Aisys CS2 stored history
Missing data on millilitres vapour used:	
 1. Datex-Ohmeda Aisys CS2 stored history

Patients will complete the QoR-15 forms pre-operatively and post-operatively. The Chief Researcher (pre-operatively) and the research assistant (post-operatively) will review the QoR-15 forms for completeness before leaving the patient's bedside. If the patient omitted any responses, they will be asked to review and complete the form.

3.6 Data Analysis & Statistical Methods

Demographic and clinical characteristics of patients will be summarised descriptively. Continuous variables (e.g. age or weight) will be summarised by mean, standard deviation, median, interquartile range, minimum and maximum values. Categorical variables (e.g. ethnicity or ASA status), will be summarised by frequency count and percentage calculations.

QoR scores will be considered as a continuous variable and will be summarised as above per treatment group (desflurane and isoflurane).

The null hypothesis for this study is that there is no statistically significant difference in mean post-operative QoR-15 scores of patients receiving isoflurane and desflurane for maintenance of anaesthesia. The alternative hypothesis is that there is a statistically significant difference in mean post-operative QoR-15 scores between patients receiving isoflurane and desflurane.

Based on the available literature, it is assumed that the quality of recovery scores will follow a normal distribution. The data will be inspected for normality prior to analysis.

For the primary objective, the mean and median difference in post-operative QoR-15 scores between the two groups will be tested for significance by the two-sided two-sample t-test and the nonparametric Wilcoxon rank sum test respectively. The mean and median difference between the pre-operative and post-operative QoR-15 scores for the two groups will also be tested for significance by the two-sided two-sample t-test and the nonparametric Wilcoxon rank sum test respectively.

For the secondary objectives, mean and median difference in consumption of vapour and time spent in recovery will be tested for significance by the t-test and Wilcoxon test as above.

Analysis, or comparisons, of subgroups of patients may be performed if it would be of clinical interest; for example, if there appears to be a significant difference in QoR scores between male and female patients.

Results will be presented in tables and graphs or verbatim, as applicable.

All statistical analyses will be performed on SAS (SAS institute Inc, Carey, NC, USA), Release 9.4 or higher, running under Microsoft Windows for a personal computer. Statistical tests will be two-sided and p values ≤ 0.05 (5%) will be considered significant.

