1.1.2 WHO Data Set

Data category	Information
Primary registry and trial identifying number	ClinicalTrials.gov: NCT04188314
Date of registration in primary registry	4 December 2019
Secondary identifying numbers	SAHPRA Phase IV Notification: N20210205
Source(s) of monetary or material support	JPRF Research Fund
Primary sponsor	JPRF Research Fund
Secondary sponsor(s)	Abbvie Scholarship
Contact for public queries	[name]: [contact]
Contact for scientific queries	[name]: [contact]
Public title	Comparing Quality of Recovery Between Desflurane & Isoflurane in Eye Surgery Patients at [name] Academic Hospital (DIQoR Trial)
Scientific title	A Randomised Control Trial to Compare Quality of Recovery between Desflurane and Isoflurane Inhalational Anaesthesia in Patients Receiving General Anaesthesia for Ophthalmological Surgery at [name] Academic Hospital (DIQoR Trial)
Countries of recruitment	South Africa
Health condition(s) or problem(s) studied	Quality of Recovery after General Anaesthesia
Intervention(s)	Control drug: Isoflurane Intervention drug: Desflurane
Key inclusion and exclusion criteria	Ages eligible for study: 18-80 years Sexes eligible for study: both Accepts healthy volunteers: no Inclusion criteria: adult patients (18-80 years), patients presenting for ophthalmological surgery under general anaesthesia, ASA I and II, able to communicate in English, Setswana or Afrikaans.

Data category	Information
	Exclusion criteria: ASA III and above, contra-indications to Laryngeal Mask Airway use during general anaesthesia, severe medical or surgical conditions who are expected to have prolonged admissions or ICU admissions, uncontrolled psychiatric conditions, known allergy or adverse reaction to volatile anaesthetics, known or suspected susceptibility to Malignant Hyperthermia, incomplete records, patients who are not treated according to the prescribed treatment protocol.
Study type	Interventional Allocation: randomised Masking: double blind (patient and observer)
Date of first enrolment	February 2020
Target sample size	180
Recruitment status	Recruiting
Primary outcome(s)	To evaluate whether there is a difference between post-operative quality of recovery in patients who received desflurane and in patients who received isoflurane for maintenance of anaesthesia, using the QoR-15 score, a patient-rated outcome measure.

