3.2.6 Outcomes

Primary outcome measures:

- Quality of recovery will be assessed in all participants with the QoR-15 score.
 - A baseline QoR-15 will be measured pre-operatively, and a repeat measurement will be done on day 1 post-operatively before discharge.
 - For each patient, the pre- and post-operative QoR-15 scores will be recorded, as well as the difference between the two measurements. The mean and median differences between the pre- and post-operative QoR-15 scores of the control group and the intervention group will be compared and tested for significance.
 - The mean and median post-operative QoR-15 scores of the control group and the intervention group will be compared and tested for significance.

[figure not shown]
Secondary outcome measures:

- To evaluate the consumption and cost of isoflurane and desflurane with a minimal or basal anaesthetic technique:
 - The vapour use per case in millilitres will be recorded from the anaesthetic machine.
 - The purchase price for isoflurane and desflurane will be obtained from the pharmacy.
 - The mean and median consumption of vapour between the two groups will be compared.
 - The mean and median cost of isoflurane and desflurane will be compared.

- To evaluate time in recovery:
 - The time the patient enters and leaves the recovery room will be recorded, as well as the total time the patient spends in the recovery room.
 - The mean and median time spent in recovery will be compared between the two groups.

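### Section 3.2.6 makes both the day-1 QoR-15 and its pre-post change primary, against the rest of the plan, and no sentence makes the extra tests supportive

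*Combined protocol and SAP*

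**What the plan says.** Section 3.2.6 has one primary heading, quality of recovery by QoR-15, with two comparisons beneath it. The first is the change score: "The mean and median differences between the pre- and post-operative QoR-15 scores of the control group and the intervention group will be compared", also to be tested for significance. The second is the post-operative score: "The mean and median post-operative QoR-15 scores of the control group and the intervention group will be compared and tested for significance".

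The rest of the plan refers to the post-operative score:

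- Section 1.1.2, registered primary outcome: "To evaluate whether there is a difference between post-operative quality of recovery in patients who received desflurane and in patients who received isoflurane".
- Section 3.1 names one primary end-point, the QoR-15 on day 1.
- Sections 2.2.2 and 3.6 state the null hypothesis as "no statistically significant difference in mean post-operative QoR-15 scores of patients receiving isoflurane and desflurane".
- Section 3.2.8 sizes the trial on a t-test of the post-operative mean.

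Section 3.6 ties the primary objective to the post-operative score ("For the primary objective, the mean and median difference in post-operative QoR-15 scores between the two groups will be tested for significance"), and pairs the mean with the t-test and the median with the Wilcoxon test. The next sentence adds the change score: "The mean and median difference between the pre-operative and post-operative QoR-15 scores for the two groups will also be tested for significance", with the same two tests. The section also says "The data will be inspected for normality prior to analysis" and "p values ≤ 0.05 (5%) will be considered significant". It gives no order among the four tests, no multiplicity adjustment, and no consequence of the normality inspection.

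**The concern.** The section that defines the outcomes gives two primary comparisons, where the design, hypothesis and sample size give one. An author who followed 3.2.6 could report a significant change score as a primary result while the post-operative comparison was not significant, and still be faithful to the protocol. Used that way, the 5% level behind the sample size would no longer hold.

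The same gap exists on a smaller scale within each outcome. Normality is to be inspected, but the plan does not say whether the result decides between the t-test and the Wilcoxon test. If the analyses disagree, no sentence says which one stands.

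**Working it through.** **Inputs from the documents.** 85 per group, SD 18.5 and difference 8 (3.2.8); two-sided 5% for each test (3.6).

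**1. Reproduce the sample size.** The normal approximation gives 2 × (1.96 + 0.8416)² × 18.5² / 8² = 83.9, so 84 per group. The exact noncentral t calculation gives 79.6% power at 84. At 85, the standard error is 18.5 × √(2/85) = 2.838 and the noncentrality is 8 / 2.838 = 2.819 on 168 degrees of freedom, so power is 80.04%. The stated 85 is therefore the answer for a t-test on the post-operative mean, and for one such test at 5%.

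**2. Type I error if only that test decides.** 5%.

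**3. Type I error if either outcome's t-test may count.** This needs the correlation between the two test statistics. Let k be the pre-operative SD divided by the post-operative SD, and ρ the correlation between pre- and post-operative scores. Then

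corr(post, change) = (1 − ρk) / √(1 + k² − 2ρk).

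The documents give neither the pre-operative SD nor ρ. I assume normal scores, a pre-operative SD of 9 to 25 and ρ of 0 to 0.9. The chance that at least one of two 5% tests rejects under the null is then a bivariate normal probability:

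| Pre-op SD | ρ | k | corr(post, change) | Either t-test significant |
|---|---|---|---|---|
| 9 | 0.9 | 0.486 | 0.936 | 6.65% |
| 9 | 0 | 0.486 | 0.899 | 7.04% |
| 18.5 | 0 | 1 | 0.707 | 8.31% |
| 18.5 | 0.5 | 1 | 0.500 | 9.07% |
| 25 | 0.7 | 1.351 | 0.056 | 9.74% |

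The third and fourth rows can be checked by hand: 1/√2 = 0.707 and 0.5/√1 = 0.5. Two independent tests would give 1 − 0.95² = 9.75%. Simulation of the whole grid (40,000 null trials per setting) gave 6.6–9.7%.

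**4. Adding the Wilcoxon tests (same simulation).** Letting either the t-test or the Wilcoxon test decide on the post-operative score alone gives 5.7–6.2%. Letting any of the four tests decide gives 7.9–11.6%.

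**5. How often the two t-tests disagree.** At a true difference of 8, simulation finds one significant and the other not in 14–34% of trials for a pre-operative SD of 12–18.5, and in 11–45% for 9–25. This matters only if both are allowed to decide.

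**The case against.** The strongest reply is that the deciding test can already be identified. The hypothesis concerns the mean post-operative score, section 3.6 pairs the mean with the t-test, section 3.2.8 uses that test, section 3.1 names one end-point, and the change score enters 3.6 only as something tested in addition. The list in 3.2.6 can itself be read as one outcome summarised in two ways. Most of this stands. A reader might infer that the plan leaves the primary test undetermined, or that its type I error simply is 7–10%. The documents do not support either inference: no passage states an either-may-count rule, and the range also depends on two inputs that the documents do not supply. What remains is that a natural reading is not a rule. Section 3.2.6 still calls the change comparison primary, and nothing makes it or the Wilcoxon tests supportive.

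A reader might also infer a design fault from the fact that an observed difference of about 5.6 (1.974 × 2.838) reaches significance below the 8-point benchmark in 2.2.2. That follows from powering any trial at 80% for its benchmark. A confidence interval can be derived from the planned means and SDs, so this is a reporting preference.

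Finally, a reader might take the statistician's lack of data access until collection ends (3.3.1) as proof that a late change is independent of the data. It is not enough. The Chief Researcher is unblinded and collects the case report forms with the allocation slips (3.3.2), stores the study documents (3.5.2) and monitors the forms and database (3.7.1).

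**Conclusion.** The point holds as an internal conflict that should be fixed before analysis. Section 3.2.6 lists two primary comparisons where the rest of the plan supports one, and section 3.6 sets no hierarchy among four tests. On the plan's own inputs, the natural primary analysis has 5% type I error and 80.0% power. If 3.2.6 is followed so that either outcome's t-test may count, type I error is about 6.6–9.7%, under normal scores and the assumed pre-operative SD and correlation. The conflict in the text does not depend on those assumptions; the size of the inflation does.

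**What to change.** In 3.2.6 and 3.6, state: *The primary analysis is the between-group difference in mean QoR-15 on day 1 after surgery, tested once by a two-sided t-test for two independent samples at the 5% level.* Move the pre-post change out of the primary list. Label the change-score and Wilcoxon results supportive and unable to alter the primary conclusion. Reporting the mean difference with its 95% confidence interval beside the 8-point benchmark is a useful option but not essential to this fix.

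The cost is wording in two sections, plus the notice to the two SMU committees that section 4 requires for changes to outcomes or analyses. Sample size, forms and data collected stay as they are, and the registered primary outcome in 1.1.2 already refers to post-operative recovery.

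The trial gives up a primary claim on the change score. At a true difference of 8 and the assumed pre-operative SDs of 9–25, that score would have about 83–97% power if the pre-post correlation were 0.7, but only 38–71% if it were 0.

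Because the Chief Researcher is unblinded and handles the data, the amendment should record that it aligns 3.2.6 with the existing hypothesis, end-point and sample size, and that it was made before any comparison by arm.

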3.2.8 Sample Size

Sample size calculation is based on estimation of the difference in mean post-operative Quality of Recovery (QoR) scores, after anaesthesia with desflurane or isoflurane. With a sample size of 85 in each group, a two-sided two-sample t-test at the 5% significance level, will have 80% power to detect a difference of 8 between the mean post-operative QoR scores with desflurane and isoflurane, assuming a standard deviation of 18.5. Sample size calculation was done on nQuery Advanced (Statistical Solutions Ltd, Cork, Ireland), Release 8.0.

A sample of 170, randomised in a 1:1 ratio to treatment with desflurane and isoflurane (85 per group) is proposed for this study.

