3.3 Assignment of Interventions

3.3.1 Allocation and Randomisation

Patients will be randomly allocated to either the control or the intervention group by computer randomisation. Randomisation and allocation will be managed remotely by the statistician, who will not be involved in patient care, and who will only gain access to study data after completion of data collection.

Block randomisation will be done to ensure that an equal number of patients are assigned to each treatment arm. Random block sizes will be used and the chief investigator, research assistant and treating anaesthetists will be blind to the size of each block.

Sequentially numbered, sealed, opaque envelopes will be prepared by the statistician. This will include a piece of paper indicating the group the patient has been randomised to. The sealed envelope will be handed to the treating anaesthetist on the day of surgery by the Chief Researcher. The Chief Researcher will be responsible for enrolment and assignment of participants.

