3.4.3 Data Collection Procedures

Patients will be assessed by the chief researcher pre-operatively on the day before surgery. The demographic information on the Data Collection Form (Section A) will be completed. Information will be obtained from the patient's file, as well as from an interview with the patient. The chief researcher will accurately measure the patient's weight and height with the available scales and measuring devices in the wards.

Patients will then be asked to complete the QoR-15 in the language of their choice, as a measure of health status over the previous 24 hours. Where possible, the QoR-15 form will be handed to the patient to complete by themselves. However, in cases where patients are visually impaired, the items on the questionnaire will be read to them, and their responses recorded.

The following day, the treating anaesthetist will complete the information about the procedure in Section B of the Data Collection Form: anaesthetic time, amount of vapour used, additional medication administered, recovery time, any adverse events (bronchospasm, laryngospasm, post-operative nausea and vomiting and/or other), and whether the prescribed anaesthetic protocol was followed.

Post-operatively, a blinded observer (research assistant) will review the patient on the day following their surgery, prior to discharge. The patients will complete the QoR-15 again.

As follow-up will be done before discharge, retention of patients to follow-up should not present any difficulties.

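### Baseline QoR-15 is collected in every patient but enters inference only through a raw change score; adjusting the day-1 comparison for it costs one degree of freedom and can only help precision

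*Combined protocol and SAP*

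**What the plan says.** Section 3.2.6 (Outcomes) states: "A baseline QoR-15 will be measured pre-operatively, and a repeat measurement will be done on day 1 post-operatively before discharge". Section 3.4.3 has patients complete the pre-operative form "as a measure of health status over the previous 24 hours", and under section 3.5.3 the staff member present "will review the QoR-15 forms for completeness before leaving the patient's bedside". The baseline should therefore be nearly complete.

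The hypothesis (sections 2.2.2 and 3.6) and the sample size (section 3.2.8) both concern the mean post-operative score. Section 3.6 tests that score without adjustment, by t-test and by Wilcoxon rank sum test. It then adds: "The mean and median difference between the pre-operative and post-operative QoR-15 scores for the two groups will also be tested for significance", using the same two tests. Section 3.2.6 places this comparison under the primary outcome measures as well: "differences between the pre- and post-operative QoR-15 scores of the control group and the intervention group will be compared and tested for significance".

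No regression model or covariate adjustment is described. The SPIRIT checklist (Appendix 6.1, item 20b) cites a page for subgroup and adjusted analyses, but section 3.6 mentions only optional subgroup comparisons.

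**The concern.** A baseline measurement of the outcome can be ignored, subtracted, or used as a covariate. The plan does the first two and omits the third, which is the most efficient.

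- **Ignoring it** is valid, but leaves in the error term whatever day-1 variation the baseline predicts.
- **Subtracting it** fixes the baseline slope at 1. If the true slope is lower, the subtraction adds noise and can cost more power than ignoring baseline would.
- **Adjusting for it** estimates the slope from the data. Under randomisation it targets the same mean difference as the stated hypothesis.

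The plan also sets two estimates of the treatment effect side by side under the primary outcome. They differ by the chance baseline difference between arms. Adjusting for baseline deals with that imbalance directly.

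**Working it through.** **Inputs from the documents.** Section 3.2.8: 85 per arm, difference 8, post-operative SD 18.5, two-sided 5%. Section 2.2.2: minimal clinically important difference (MCID) 8.

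**Inputs not in the documents (assumed).** Pre-post correlation r from 0 to 0.6; ratio k = SD_pre/SD_post of 1, 0.8 or 0.6.

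**1. Reproduce the plan's figure.** Section 3.2.8 states that "a two-sided two-sample t-test at the 5% significance level, will have 80% power". The standard error of the difference is 18.5 × √(2/85) = 2.84, so the noncentrality is 8/2.84 = 2.82. With 168 df the noncentral t gives power 0.800, which agrees. The registration data set in section 1.1.2 gives 180 under "Target sample size"; at 90 per arm (178 df) power would be 0.823. The discrepancy does not affect this point.

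**2. Standard deviation that each analysis works with.**
- Day-1 score alone: 18.5
- ANCOVA: 18.5 × √(1 − r²), with 167 df
- Change score: 18.5 × √(1 + k² − 2rk), with 168 df

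The ANCOVA figure does not depend on k. Since (1 + k² − 2rk) − (1 − r²) = (k − r)², which is never negative, ANCOVA variance cannot exceed change-score variance, apart from the one df. The change score is worse than ignoring baseline when k² − 2rk > 0, that is, when r < k/2. The break-even r is 0.5, 0.4 or 0.3 for k = 1, 0.8 or 0.6.

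**3. Power at 85 per arm for a difference of 8.** The unadjusted day-1 test has 80.0% throughout.

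| r | ANCOVA SD | ANCOVA power | Change score, k = 1 | Change score, k = 0.8 | Change score, k = 0.6 |
|---|---|---|---|---|---|
| 0 | 18.50 | 80.0% | 51% | 59% | 67% |
| 0.1 | 18.41 | 80.4% | 55% | 63% | 71% |
| 0.2 | 18.13 | 81.6% | 60% | 68% | 75% |
| 0.3 | 17.65 | 83.6% | 66% | 74% | 80% |
| 0.5 | 16.02 | 89.9% | 80% | 86% | 90% |
| 0.6 | 14.80 | 93.9% | 88% | 92% | 94% |

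**4. The gain as sample size.** Equivalent unadjusted n per arm is 85/(1 − r²): 85.9 at r = 0.1, 93.4 at r = 0.3 and 113.3 at r = 0.5.

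**5. Gap between the two planned estimates.** The change-score estimate equals the day-1 estimate minus the baseline difference between arms. That difference has expectation zero and standard error k × 18.5 × √(2/85), which is 2.84 at k = 1. The 95% range is ±1.96 × 2.84 = ±5.6 points at k = 1, ±4.4 at k = 0.8 and ±3.3 at k = 0.6, against the MCID of 8.

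**The case against.** The strongest reply is that nothing is broken. Hypothesis, sample size and primary t-test all concern the day-1 score, and the test is unbiased with the stated power. The benefit depends on an r that the documents do not supply. At r = 0.1, 0.2 and 0.3 the half-width of the 95% interval falls only from 5.60 points to 5.57, 5.49 and 5.34. Some design features could keep r low: a fairly homogeneous ASA I–II population, different staff handling the two forms, and items read aloud to patients who cannot see to complete them. All of this stands. It limits the claim to an improvement of unknown size, but it is no reason to decline one that costs a single df.

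It is also true that ANCOVA is not needed to settle which analysis decides the trial; naming the existing day-1 t-test as the sole primary analysis would do that. ANCOVA does so while also using the baseline.

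The third objection is timing. By the timeline in section 1.5, data collection ends in July 2021, and the latest amendment is dated April 2021. The Chief Researcher is not blinded and holds the case report forms with the allocation slips. A late change to the primary analysis therefore needs a dated record and a stated reason. The statistician, however, "will only gain access to study data after completion of data collection", so the model can still be fixed before that release.

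Adjustment should not cost patients: sections 3.2.2 and 3.8 already exclude incomplete records.

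**Conclusion.** The point holds as a recommended improvement, not as a correction of an error. The planned day-1 t-test is valid and its 80% power reproduces. Adjusting for baseline leaves power at 80.0% if r is 0 and raises it to 83.6% at r = 0.3, 89.9% at 0.5 and 93.9% at 0.6. These figures assume 85 per arm, a difference of 8, a post-operative SD of 18.5 and a linear relation between the two scores. Because r is unknown, the gain can be described only as lying between nil and substantial.

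The raw change score is the weakest of the three analyses when r is below half the ratio of baseline to day-1 SD. Its power at low r depends heavily on that ratio, which the documents do not give either.

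**What to change.** In section 3.6, specify one primary analysis: a linear model of day-1 QoR-15 on treatment group, with pre-operative QoR-15 as the only covariate, reporting the adjusted mean difference, its 95% confidence interval and p-value. Keep the unadjusted t-test and the Wilcoxon test on the day-1 score as sensitivity analyses. Make the change score descriptive or supportive, and reword section 3.2.6 to match.

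Date the amendment and give its reason before data are released to the statistician, and notify the SMU Research Committee and the SMU Research Ethics Committee, as section 4 requires for changes to analyses.

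The cost is one degree of freedom, one amendment to two sections and the two notifications. No additional patients, visits or data are needed.
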